3.1.2. Dose limiting toxicity (DLT)

A dose limiting toxicity (DLT) is defined as a grade 3 or higher adverse event as defined by the Division of AIDS Toxicity Table for Severe Adult and Pediatric Adverse Events (including signs/symptoms, lab toxicities and/or clinical events) considered by a safety review board as probably or definitely related to study treatment. The first four patients (regardless of the dose) will be enrolled first and followed up for at least 2 weeks of treatment. If more than 2 DLTs occur of the first four treated patients, then the enrolment of additional patients will be stopped, otherwise the enrolment of planned patients will be confirmed.

In addition, in case of a life threatening (grade 4) adverse reaction enrolment and treatment of ongoing patients will be immediately discontinued.

In both cases, enrolment will only be resumed upon the decision of the sponsor if the Data Safety Monitoring Board can conclude that the causality of the event was unrelated or unlikely related to study treatment.

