	At 150mg, the DSMB will meet every 4 patients in order to review on a regular basis th safety profile of this dose level and to recommend, if appropriate, the continuation of th study.	
	The sample size at a dose level will not be changed (i.e. 28 patients will need to b randomized receiving the same dose).	
	Dose limiting toxicity (DLT) is defined as a grade 3 or higher adverse event as defined b the "Division of AIDS table for grading the severity of adult and pediatric adverse events (including signs/symptoms, lab toxicities and/or clinical events) considered by the Dat Safety Monitoring Board as probably or definitely related to study treatment.	
	If more than 2 DLTs occur during the treatment period of the first four treated patient	

Study n° ABX4	464-004 Clinical Phase IIa Type of Study Safety Study
	(regardless of the dose), then the enrolment of additional patients will be stopped. In addition, in case of a life threatening (grade 4) adverse reaction enrolment and treatment of ongoing patients will be immediately discontinued. In both cases, enrolment will only be resumed upon the decision of the sponsor if the Data Safety Monitoring Board can conclude that the causality of the event was unrelated or unlikely related to study treatment.
	At day 29, DRV/RTV or DRV/COBI and ABX464 or its matching placebo (i.e. all treatments) will be stopped. The viral load will be monitored twice a week during the first three weeks and weekly during the next weeks. In case of Viral Rebound (VR; defined below), ART will be resumed.
	Thorough pharmacokinetics analysis will be performed to characterize potential drug-drug interactions between ABX464 and DRV/RTV-COBI.
	The study design is summarized below in this chart.
	D-21 vísit D0 vísit D7 vísit D14 vísit D21 vísit D25 vísit D28 vísit D29 Every week Folíow-up Vísits Vísit Screening ARTs ART interruption Reintroduction * * * * * * * * * * * * * * *
	D-21 D0 D29
	Designer - ssee Dennavir / Filoravisos Gobicistat
	ABX164 br/Placebo Streeving Batcline / Randomiation Batcline / Randomiation Batcline / Randomiation
	Safe sex counseling will be offered at every study visit in order to inform the patient about potential infectiousness since the viral load can rebound.

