3. INVESTIGATIONAL PLAN

3.1. Study design

3.1.1. Design and methodology

This study is a placebo-controlled study aimed at assessing the safety of ABX464 administered at 50 mg o.d. (or potentially at 150 mg o.d.) versus placebo in HIV infected patients who are treated with darunavir + ritonavir (DRV/RTV) or darunavir + cobicistat (DRV/COBI). Eligible patients should be treated with darunavir + ritonavir or darunavir + cobicistat as monotherapy for at least 8 weeks prior to baseline. Patients should be fully suppressed (< 50 copies/mL) for at least 6 months prior to enrolment.

Upon screening visit, eligible patients will continue DRV/RTV or DRV/COBI single regimen given respectively at 800 mg of darunavir with 100 mg of ritonavir or 150 mg of cobicistat once a day with food in the morning.

At Day 0, study drug (ABX464 or its matching placebo) will be added on top of this background therapy for the next 28 days. ABX464 or its matching placebo will be given once a day at the fixed dose of 50 mg (or potentially at 150 mg o.d.).

A 3:1 randomization ratio will be applied meaning that, per treatment block, 3 patients will receive ABX464 on top of DRV/RTV or DRV/COBI and 1 patient will receive placebo on top of DRV/RTV or DRV/COBI.

The original fixed dose (i.e. 50mg o.d.) of the study drug has been selected in November 2015 based on the reassuring safety data accumulated on the 50 mg o.d. and the concentrations in ABX464-N-glucuronide, the active metabolite of ABX464. However, in January 2016, the results of first phase IIa study conducted in treatment-naïve HIV infected patients with high viral load upon enrolment (5,000-500,000 copies/mL) confirmed the antiviral activity of ABX464 at higher doses. A reduction of viral load > 0.5 log was observed in 3/12 patients in the 75 and 100 mg cohorts and 4/6 patients in the 150 mg cohort, demonstrating a dose relationship effect of ABX464.

In case the first 8 patients treated for 28 days at 50mg o.d. in the present study (i.e. two first randomization blocks) do not show a DLT, the study protocol plans to study the 150 mg dose. The DSMB will specifically meet once the first 8 patients have been treated for 28 days in order to recommend, if appropriate, a dose increase to 150mg o.d.

At 150mg, the DSMB will meet every 4 patients in order to review on a regular basis the safety profile of this dose level and to recommend, if appropriate, the continuation of the study.

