The sample size at a dose level will not be changed (i.e. 28 patients will need to be randomized receiving the same dose).

Dose limiting toxicity (DLT) is defined as a grade 3 or higher adverse event as defined by the "Division of AIDS table for grading the severity of adult and pediatric adverse events" (including signs/symptoms, lab toxicities and/or clinical events) considered by the Data Safety Monitoring Board as probably or definitely related to study treatment.

If more than 2 DLTs occur during the treatment period of the first four treated patients (regardless of the dose), then the enrolment of additional patients will be stopped. In addition, in case of a life threatening (grade 4) adverse reaction enrolment and treatment of ongoing patients will be immediately discontinued. In both cases, enrolment will only be resumed upon the decision of the sponsor if the Data Safety Monitoring Board can conclude that the causality of the event was unrelated or unlikely related to study treatment.

At day 29, DRV/RTV or DRV/COBI and ABX464 or its matching placebo (i.e. all treatments) will be stopped. The viral load will be monitored twice a week during the first three weeks and weekly during the next weeks. In case of Viral Rebound (VR; defined below), ART will be resumed.

Thorough pharmacokinetics analysis will be performed to characterize potential drug-drug interactions between ABX464 and DRV/RTV-COBI.

The study design is summarized below in this chart.

Clinical Study Protocol

Study code: ABX464-004

Safe sex counseling will be offered at every study visit in order to inform the patient about potential infectiousness since the viral load can rebound.

In this open-ended study, the study visits will be performed every week until Viral Rebound and then reintroduction of ARTs.

A viral load and a CD4+ count will be assessed weekly during the course of the study. However, these testings will be performed twice a week during the first three weeks following treatment interruption in order to capture as early as possible a potential early relapse.

A Viral Rebound (VR) is defined as HIV viral load > 1000 copies mL-1. If a patient meets this criterion, then ARTs should be reintroduced. The patient should be withdrawn from the study and should perform a follow-up visits every 14 days after ARTs reintroduction until the viral load has returned to undetectable levels.

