11.4. Randomization

Randomization will be centrally managed by block of 4 patients (3 ABX464/1 placebo). It will be performed via the eCRF. The bottle numbers to be used for a specific patient will assign according to a pre-defined randomization list by SODIA. This information will be provided to the site by fax.

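### With two of the three ABX464 patients in the first block having a related grade 3 DLT, the written rule confirms enrolment; add a pause at two patients with a DLT, at each dose

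*Protocol*

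**What the plan says.** Protocol section 3.1.2 holds the rule: "If more than 2 DLTs occur of the first four treated patients, then the enrolment of additional patients will be stopped". The sentence continues "otherwise the enrolment of planned patients will be confirmed". The observation period there is "The first four patients (regardless of the dose) will be enrolled first and followed up for at least 2 weeks of treatment". Section 3.1.1 states the rule over a different period: "If more than 2 DLTs occur during the treatment period of the first four treated patients (regardless of the dose"; the synopsis does the same.

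Allocation is fixed in section 11.4, "Randomization will be centrally managed by block of 4 patients (3 ABX464/1 placebo", and in section 3.1.1, "per treatment block, 3 patients will receive ABX464 on top of DRV/RTV or DRV/COBI and 1 patient will receive placebo".

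The other safeguards are these:

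- One grade 4 adverse reaction halts enrolment and ongoing treatment (3.1.1, 3.1.2).
- Escalation to 150 mg requires no DLT in the first eight patients at 50 mg (3.1.1, 3.1.3).
- The DSMB meets once the first four patients have had at least two weeks of treatment and then after every four. It may advise termination at any time, but the sponsor decides (3.1.3).
- At 150 mg the DSMB meets every four patients to review safety "and to recommend, if appropriate, the continuation of the study" (3.1.1).
- A patient whose transaminases or alkaline phosphatase reach 2.0 x ULN is withdrawn (7.2).

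**The concern.** The threshold is set for four patients, but only three of a fully treated first block receive ABX464. If patients are counted and the placebo patient has no DLT, every exposed patient must have a DLT before the rule acts. Two of three exposed patients with a DLT is an observed rate of 67%, and the written outcome is then to confirm enrolment. If no halt is advised and accepted, the next block puts three more patients on ABX464 before the next scheduled review.

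Three wordings also leave the action open:

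- The rule does not say whether it counts patients or events.
- It is unclear whether the rule starts again at 150 mg. The trial's first four treated patients are at 50 mg, so on a literal reading 150 mg has reviews but no DLT-count stop.
- Section 3.1.2 allows the decision after two weeks, while section 3.1.1 counts DLTs over the whole treatment period.

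**Working it through.** The protocol gives no operating characteristic for the rule, so there is no figure to reproduce.

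**Inputs.** From the protocol: stop at 3 or more DLTs in the first four; 3 ABX464 and 1 placebo per block; no DLT in eight patients before 150 mg. Assumed, because the protocol gives no DLT rate: per-patient rate p on ABX464 of 20%, 33% or 50%; rate q on placebo of 0 or 10%; independent patients; the whole block treated.

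**1. The scenario.** Two patients with one DLT each make 2 DLTs, and 2 is not more than 2, so enrolment is confirmed. The observed rate is 2/3 = 67%. The exact one-sided 95% lower limit solves 3p² − 2p³ = 0.05, giving p = 13.5%.

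**2. Present rule, patients counted.**
- q = 0: P(stop) = p³. At 50%: 0.5³ = 12.5%.
- q = 10%: P(stop) = p³ + q·3p²(1−p). At 50%: 0.125 + 0.1 × 0.375 = 16.3%.

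**3. Present rule, events counted.** With no placebo DLT and a Poisson number of events with mean m = −3 ln(1−p), P(stop) = 1 − e^(−m)(1 + m + m²/2). At 50%: m = 2.079, giving 34.5%.

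**4. Pause at two or more patients.**
- q = 0: P(pause) = 3p²(1−p) + p³. At 33%: 0.2189 + 0.0359 = 25.5%.
- q = 10%: add q·3p(1−p)². At 33%: 0.2548 + 0.1 × 0.4444 = 29.9%.

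| Chance that the DLT-count trigger acts | p = 20% | p = 33% | p = 50% |
|---|---|---|---|
| Present stop, patients, q = 0 | 0.8% | 3.6% | 12.5% |
| Present stop, patients, q = 10% | 1.8% | 5.8% | 16.3% |
| Present stop, events, q = 0 | 3.1% | 12.1% | 34.5% |
| Pause at 2 or more patients, q = 0 | 10.4% | 25.5% | 50.0% |
| Pause at 2 or more patients, q = 10% | 14.2% | 29.9% | 53.8% |

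**5. Needless pauses at a tolerable true rate of 10%.**
- Per block, q = 0: 3 × 0.01 × 0.9 + 0.001 = 2.8%.
- Per block, q = p: 1 − 0.9⁴ − 4 × 0.1 × 0.9³ = 5.2%.
- Both doses, with 150 mg opened only after no DLT in the first eight: 0.028 × (1 + 0.9⁶) = 4.3% for q = 0, and 0.0523 × (1 + 0.9⁸) = 7.5% for q = p.

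**6. Effect of the grade 4 stop, for illustration.** Assume p = 50%, q = 0, patients counted, and one DLT in five of grade 4. Each exposed patient then has a 10% chance of a grade 4 DLT and a 40% chance of a grade 3 DLT only.
- Present automatic stops together: (1 − 0.9³) + 0.4³ = 27.1% + 6.4% = 33.5%.
- With the pause added: 27.1% + 3 × 0.4² × 0.5 + 0.4³ = 27.1% + 24.0% + 6.4% = 57.5%.
- The gap is 24 points, against 50.0% − 12.5% = 37.5 points for the count alone.

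**The case against.** The strongest objection is that an independent review already takes place here. The first four patients are enrolled ahead of the rest, the DSMB meets after their first two weeks, and an event is a DLT only once the board has judged it probably or definitely related. A reader might infer from the rule that two DLTs could pass unreviewed, or that the trial would certainly go on. The documents do not support either reading: the board must know of both events and may advise termination at any time. What the protocol lacks is a binding consequence. The board's advice is consultative, and advice to halt would contradict the written confirmation.

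A reader might also take 12.5% as the whole chance of a halt at a 50% DLT rate. It is not. It leaves out the grade 4 stop and any discretionary DSMB action, which raise the chance under both the present and the proposed rule. Step 6 shows a smaller gap, but one that remains. Counting events narrows it too.

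The remaining safeguards do not cover the case. The escalation condition blocks 150 mg but does not pause 50 mg enrolment, and the liver-enzyme criterion withdraws individual patients only. The 150 mg reviews are real but have no numeric threshold in the protocol.

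It is also fair to say that the threshold is a design choice, that both doses had been given before (section 3.1.1), and that the DSMB charter, not shown here, may hold a limit. A stricter charter would still conflict with the protocol's wording.

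**Conclusion.** The point holds in a limited form. The numeric rule confirms enrolment when two of the three ABX464 patients in the first block each have one related grade 3 DLT, and no other provision imposes a halt in that case. For the count alone, a pause at two patients would raise the chance of action from 0.8% to 10.4%, from 3.6% to 25.5% and from 12.5% to 50.0% at assumed DLT rates of 20%, 33% and 50%. These figures count patients and assume no placebo DLT, independent patients and a fully treated first block.

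The pause would still miss about three in four first blocks at a 33% rate, so it adds to DSMB review and does not replace it. It is an inexpensive improvement that should be made in a trial whose primary objective is safety. The exact threshold remains a matter of judgement.

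**What to change.** Amend the synopsis and sections 3.1.1 and 3.1.2 as follows.

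- **Add a pause.** At each dose level (50 mg and again at 150 mg), if two or more patients in the first block of four have at least one DLT at any time in the 28-day treatment period, enrolment and new treatment starts are paused at once, even if the next block has opened. They resume only after a documented DSMB recommendation to resume. The present resumption condition would not serve here, because it asks the board to find unrelated, or unlikely to be related, an event that it has already judged probably or definitely related.
- **Clarify the existing stop.** State that the stop at more than two DLTs counts events, so that three DLTs in one patient still trigger it. Keep it and the grade 4 stop.
- **Replace the clause that confirms enrolment.** If neither the stop nor the pause criterion is met at the two-week DSMB review, enrolment is confirmed, subject to the pause rule for DLTs arising up to Day 28. This covers DLTs on days 15 to 28, after that review.
- **Keep the no-DLT condition for escalation**, and align the DSMB charter.

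The cost is a protocol amendment and a charter alignment, with no extra patients and no unblinding of the sponsor. For DLTs in the first two weeks at 50 mg, the pause can use the DSMB meeting already scheduled; later DLTs may need an extra one. At a true 10% DLT rate, a needless pause would occur somewhere over both doses in 4.3% to 7.5% of trials.

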3.1.3. Data Safety Monitoring Board

An independent Data Safety Monitoring Board (iDSMB), with expertise and experience in the pathology, and without direct involvement in the conduct of the trial, will be set up specifically to guarantee effective protection of patients, insure the ethical conduct of the trial, benefit/risk ratio of the trial, and to ensure the independent review of the scientific results during the trial and at the end of the trial.

The DSMB will meet first after the 4 first patients are enrolled and treated for at least 2 weeks and then every group of 4 patients. Besides, the DSMB may recommend the early termination of the trial at any time if an unacceptable toxicity occurs.

In addition, the DSMB will meet specifically once the first 8 patients are treated with the 50mg o.d. for 28 days. If none of these patients experience a DLT, then the DSMB can recommend a dose escalation to 150mg o.d.

Clinical Study Protocol

The DSMB has only a consultative role; it will inform the sponsor who will decide whether the DSMB recommendation will be followed. A DSMB charter must be available upon submission of the trial (initial protocol) to the respective competent authorities.

3.2. Duration of study participation

From a patient standpoint, the study participation is defined as

- Two to four weeks of screening period;
- Four weeks as combination treatment period (DRV/RTV or DRV/COBI + ABX464/placebo);
- A treatment interruption period that will last until the viral load rebounds.
- Some follow-up visits, every 14 days, after ARTs reintroduction until the viral load has returned to undetectable levels. In any case, the liver function testings should be peformed during these visits for at least 28 days after treatment interruption or premature study discontinuation.

Overall, the minimal study duration will be 49 days.

In case of no Viral Rebound then the end of study will be 3 months after treatment interruption with the possibility for the patient to be enrolled in long term-observational follow-up study.

4. STUDY POPULATION

4.1. Number of Patients/Centers

28 to 36 patients overall will be enrolled in this study. These patients will be enrolled in up to 8 sites located in France, Belgium and Spain.

4.2. Eligibility Criteria

4.2.1. Inclusion Criteria

A patient will be eligible for inclusion in this study only if ALL of the following criteria apply:

- 1. Patients infected with HIV;
- Patients with HIV plasma viral load ≤ 50 copies mL⁻¹ during the 6 months prior to screening with a maximum of 2 blips during this period;
- 3. Patients treated by DRV/RTV or DRV/COBI for at least 8 weeks prior to baseline;
- Patients' HIV plasma viral load ≤ 100,000 copies mL⁻¹ at any time (apart from primary infection if recorded);
- 5. Patients' CD4+ T cells count ≥ 250 cells per mm³ at any time since diagnosis;
- 6. Patients with CD4+ T cells count \geq 600 cells per mm³ at screening;
- 7. Man or woman aged 18-65 years;
- 8. Patients with hematological and biochemical laboratory parameters as follows and within 7 days of baseline:
 - Hemoglobin > 9.0 g dL⁻¹;
 - Absolute neutrophil count \geq 750 mm⁻³;
 - Platelets \geq 100,000 mm⁻³;
 - Total serum creatinine ≤ 1.3 x ULN (upper limit of normal);
 - Creatinine clearance > 50 mL min⁻¹ by the Cockcroft-Gault equation within 60 days of entry;
 - Total serum bilirubin < 2.0 x ULN;
 - Alkaline phosphatase, AST (SGOT) and ALT (SGPT) < 1.5 x ULN;
 - Serum lipase less than or equal to 2.0 x ULN;
- 9. Patients should be able and willing to comply with study visits and procedures as per protocol;
- 10. Patients should understand, sign and date the written voluntary informed consent form at the screening visit prior to any protocol-specific procedures being performed;
- 11. Patients should be affiliated to a social security regimen (for French sites only);
- 12. Females and males receiving the study treatment and their partners must agree to use a highly effective contraceptive method during the study and for 3 months after end of study or early termination. Contraception should be in place at least 2 weeks prior to study participation. Women must be surgically sterile or if of childbearing potential must use a highly effective contraceptive method. Women of childbearing potential (WOCBP) will enter the study after confirmed menstrual period and a negative pregnancy test. Highly effective methods of contraception include true abstinence, intrauterine device (IUD) or hormonal contraception associated with inhibition of ovulation, intrauterine hormone releasing system, bilateral tubal occlusion, vasectomized partner. True abstinence is defined when this is in line with the preferred and usual lifestyle of the patient. In each case of delayed menstrual period (over one month between menstruations) confirmation of absence of pregnancy is required. This recommendation also applies to WOCBP with infrequent or irregular menstrual cycle.

4.2.2. Exclusion Criteria

The following criteria should be checked at the time of screening. If ANY exclusion criterion applies, the subject will not be included in the study:

- 1. Patient displaying any HIV protease inhibitor resistance mutation as listed in the current version of the HIV drug resistance database (Stanford University);
- 2. Patient having undergone virological failure as defined by a viral load ≥ 500 copies mL-1 confirmed by a second measure since initiation of the ART;
- 3. History of an AIDS-defining clinical illness;
- 4. Concomitant AIDS-related opportunistic disease;
- 5. History of allergic disease, anaphylaxis or reactions likely to be triggered or exacerbated by any component of the study drug;
- 6. Acute or chronic infectious disease other than HIV infection (include but not limited to viral hepatitis such as hepatitis B, active tuberculosis, active syphilis [i.e. currently treated], HTLV-1, HTLV-2). Of note co infection with hepatitis C is allowed providing their liver function parameters are within the following ranges: platelet > 150.000/mm3; γGT ≤ 2.5 ULN; Albumin > 40 g/L and providing that they are not receiving specific treatment during the study that could interfere with the study objectives;
- Acute, chronic or history of clinically relevant pulmonary, cardiovascular, gastrointestinal, hepatic, pancreatic or renal functional abnormality, encephalopathy, neuropathy or unstable CNS pathology, angina or cardiac arrhythmias, or any other clinically significant medical problems as determined by physical examination and/or laboratory screening tests and/or medical history;
- 8. Uncontrolled dyslipidemia;
- 9. Acute, chronic or history of immunodeficiency or autoimmune disease other than HIV infection;
- 10. Unstable asthma (defined as sudden acute attacks occurring in less than three hours without an obvious trigger, hospitalization for asthma in the last two years); food or wine induced asthma;
- 11. History of malignancy unless there has been surgical excision that is considered to have achieved cure;
- 12. Active malignancy that may require chemotherapy or radiation therapy;
- 13. Seizure disorder or any history of prior seizure;
- 14. Serious illness requiring systemic treatment and/or hospitalization within 7 days prior to baseline;
- 15. Pregnant or breast-feeding woman;
- 16. Active drug or alcohol abuse or dependence;
- 17. Use of any investigational or non-registered product within 3 months preceding baseline;
- 18. Any condition, which in the opinion of the investigator, could compromise the subject's safety or adherence to the study protocol.

